5.1 Outcome definitions

5.1.1. Primary outcome:

The primary outcome is new symptomatic sICH (fatal or non-fatal) found on CT scan, MRI scan or by autopsy over at least two years follow-up. We will perform analysis of time to first event after two years follow-up as primary analysis and after total follow-up time as

secondary analysis. Those not experiencing the event will be censored at last available follow-up, death unrelated to a primary outcome or voluntary withdrawal from the trial (whichever occurs soonest).

5.1.2. Secondary outcomes:

Secondary outcomes will be analysed as composite endpoints except for functional outcome at two years (according to modified Rankin Scale) and death of any cause. The secondary endpoints will also be reported individually. Secondary outcomes will be analysed as reported by investigator.

5.1.2.1 Composite secondary outcomes:

The following composite endpoints will be analysed:

- **Major ischaemic events:** Ischaemic stroke, myocardial infarction, mesenteric ischaemia, peripheral arterial occlusion, deep vein thrombosis, pulmonary embolism, revascularisation procedures (carotid, coronary or peripheral)
- **Major haemorrhagic events:** symptomatic intracerebral haemorrhage, other symptomatic intracranial haemorrhages (epidural, subdural or subarachnoid haemorrhages both spontaneous and traumatic), symptomatic major extracranial haemorrhage requiring transfusion with more than 2 units of whole blood or red cells, a fall in > 2.0 g/L haemoglobin, bleeding in a critical area or organ (intraspinal, intraocular, retroperitoneal, intra-articular or pericardial, or intramuscular with compartment syndrome) or haemorrhage leading to death.
- **Major adverse cardiovascular events (MACE)** defined as ischaemic stroke, myocardial infarction, other major ischaemic events, intracerebral haemorrhage, other intracranial haemorrhage, major extracranial haemorrhage or vascular death.

Time to event for secondary outcomes except for functional outcome according to modified Rankin Scale will be defined in the same way as for primary outcome. Modified Rankin Scale is not subject to survival analysis and thus time to event is irrelevant for this outcome.

As for the primary outcome, secondary outcomes will be analysed as time to first event after two-years follow-up and after total follow-up time.

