5.2.2. Secondary analyses

Secondary dichotomous composite outcomes will be analysed using the same statistical approach as primary outcome, i.e. by Kaplan-Meier curves, log-rank test, and Cox PH model. Ordinal outcome of function (modified Rankin Scale) will be analysed by an ordinal logistic regression model if the proportional odds assumption is confirmed. Adjustments for covariates will be performed in the same manner as for primary analysis.

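### The haemoglobin criterion for major extracranial haemorrhage is printed as a fall of more than 2.0 g/L (0.2 g/dL), probably a unit slip, so a symptomatic bleed with a trivial fall can count as major haemorrhage and as MACE

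*SAP*

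**What the plan says.** SAP section 5.1.2.1 defines the composite of major haemorrhagic events. Its extracranial part covers symptomatic bleeds "requiring transfusion with more than 2 units of whole blood or red cells, a fall in > 2.0 g/L haemoglobin", then names bleeding at critical sites, and closes with "or intramuscular with compartment syndrome) or haemorrhage leading to death". The items are joined by commas and a final 'or', so any one of them is enough.

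The MACE definition in the same section ends with "major extracranial haemorrhage or vascular death", so the extracranial criteria carry over to MACE.

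On the source of the events, section 5.1.2 states: "Secondary outcomes will be analysed as reported by investigator". On the analysis, section 5.1.2.1 says that "secondary outcomes will be analysed as time to first event after two-years follow-up and after total follow-up time", and section 5.2.2 adds: "Secondary dichotomous composite outcomes will be analysed using the same statistical approach as primary outcome", that is, Kaplan-Meier curves, log-rank test and Cox model.

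The haemoglobin threshold appears only once in the SAP. No other section repeats, explains or corrects it.

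**The concern.** A haemoglobin fall of 2.0 g/L is very small, and the other criteria in the list describe serious bleeding. One criterion that is far looser than its neighbours comes close to setting the definition alone: almost any symptomatic extracranial bleed with two haemoglobin readings could qualify, and the transfusion criterion would add little.

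Two of the three secondary composites are exposed. Because both are analysed as time to first event, a minor bleed counted as major would also set the MACE time of a participant who later had a stroke or infarction. That participant is a MACE case either way, but the event would be dated to the bleed. The analyses are run separately in the antiplatelet and anticoagulant trials (section 5.2), neither of which had its own sample size estimate (section 2.4). Section 5.2.1 itself allows for few events when covariates are chosen. With small counts, a handful of misclassified bleeds could move an estimate.

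**Working it through.** The threshold is a definition, so the plan has no derived figure to reproduce. The check is a unit conversion, a comparison with the neighbouring criterion, and an illustration of how well the printed limit separates bleeds. Only the 2.0 g/L and the 2 units come from the SAP (section 5.1.2.1); every other input is an assumption and is marked as such.

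**1. Conversion.** 1 g/dL = 10 g/L, so 2.0 g/L = 0.2 g/dL. At an assumed haemoglobin of 140 g/L this is 2/140 = 1.4%. Over an assumed range of 100 to 160 g/L it is 2.0% to 1.25%. Had the unit been g/dL, the limit would be 20 g/L, ten times larger, or 20% to 12.5% over the same range.

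**2. Comparison with the transfusion criterion.** Assume that one red-cell unit corresponds to 5 to 15 g/L.
- At the 2-unit boundary: 2 × 5 = 10 to 2 × 15 = 30 g/L. Divided by 2 g/L, the ratio is 5 to 15.
- The SAP requires more than 2 units, so at least 3 whole units: 15 to 45 g/L, a ratio of 7.5 to 22.5.

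On either reading the haemoglobin limit is several times looser than the transfusion limit beside it.

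**3. Noise alone (no true fall).** Assume haemoglobin of 120 to 140 g/L and a coefficient of variation (CV) of 1% to 4% per reading. The difference of two readings has SD √2 × CV × haemoglobin, and P(fall > c) = 1 − Φ(c/SD of the difference).
- 120 g/L, CV 1%: SD 1.70, P(> 2 g/L) = 11.9%.
- 140 g/L, CV 4%: SD 7.92, P(> 2 g/L) = 40.0%.
- P(> 20 g/L) is at most 0.6% anywhere in this range.

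**4. A symptomatic bleed with a small true fall d.** With SD per reading of 2, 4 or 6 g/L (assumed), P(measured fall > c) = 1 − Φ((c − d)/(√2 × SD)).

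| True fall d | SD per reading | P(> 2 g/L) | P(> 20 g/L) |
|---|---|---|---|
| 5 g/L | 2 | 85.6% | 0.0% |
| 5 g/L | 4 | 70.2% | 0.4% |
| 5 g/L | 6 | 63.8% | 3.9% |
| 10 g/L | 2 | 99.8% | 0.02% |
| 10 g/L | 4 | 92.1% | 3.9% |
| 10 g/L | 6 | 82.7% | 11.9% |

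One line in full: d = 5, SD = 2, c = 2 gives (2 − 5)/(1.414 × 2) = −1.06, and 1 − Φ(−1.06) = 85.6%.

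Under these assumptions the printed limit lies within plausible measurement variation and accepts most small bleeds, whereas a limit ten times larger rejects most of them. The tables describe the criterion, not the trial: the SAP gives no expected event rates for these composites, so no count of affected events follows.

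**The case against.** The strongest reply is that a misprint in the SAP need not reach the results. Secondary outcomes are taken as the investigator reported them, and the SAP describes no step in which bleeds are reclassified against the printed 2.0 g/L. If the case report form carried a different unit, the data are sound and only the SAP text is wrong. This stands as a limit on the consequence: the effect on the results may be nil. It does not remove the defect, because the published endpoint definition would then not match what was counted. If investigators did work to the printed limit, events are misclassified. The SAP alone cannot show which applies.

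The criterion also applies only to symptomatic extracranial haemorrhage; intracranial, critical-site, fatal and transfused bleeds do not depend on the unit. That is correct and narrows the scope. The word 'major' in the definition gives no further protection, since the listed criteria are what define it. Section 5.1.2 has the secondary endpoints reported individually as well, so an excess of extracranial bleeds within a composite would be partly visible. That helps a reader of the results but does not correct the log-rank and Cox tests of the composites.

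Finally, the displacement of a later stroke or infarction requires a bleed classed on haemoglobin alone and a later event in the same participant. It is a possibility, not an expected effect.

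**Conclusion.** The concern holds. As printed, the haemoglobin criterion is out of line with every other item in the same definition, and nothing in the SAP explains it. A g/L written for g/dL is the probable cause, but this is inferred from the mismatch and not proven; the intended value must come from the sponsor.

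The size of the error in the criterion is clear: a factor of ten if the unit slipped. The size of the error in the results is not known, may be zero, and could go in either direction. It is confined to the major haemorrhagic and MACE composites; the primary outcome of new symptomatic sICH and the sample size of 500 do not depend on it. The conversion is exact. The comparison with transfusion and the probabilities rest on the stated assumptions about haemoglobin level, measurement variation and the equivalent of one red-cell unit. The point should be fixed before analysis.

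**What to change.** - Confirm the threshold and its unit against the protocol and the definition on the case report form.
- Correct section 5.1.2.1 accordingly: to more than 2.0 g/dL (20 g/L) if that was intended. If 2.0 g/L was really meant, say so and justify it.
- List any extracranial bleeds classed as major on the haemoglobin criterion alone, re-check them against the confirmed threshold, and carry any change through to both the major haemorrhagic and the MACE composites, including the date of first event.

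The cost is one unit in the SAP, plus a re-check of however many such bleeds there are, possibly none.

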5.2 Analysis methods

Analyses will be performed separately for participants included in the antiplatelet trial and participants included in the anticoagulant trial.

5.2.1 Primary analysis

Primary analysis is a comparison between groups of time-to-first event of new symptomatic sICH during two-year follow-up. This will be assessed by generating life tables, Kaplan-Meier curves and applying log-rank test.

The sample size calculation, performed before the study was started, is based on comparisons of proportions. However, in the protocol (latest protocol version v210421), time-to-event-analysis is defined as primary analysis. We will follow the protocol.

To adjust the differences between the groups, Cox proportional hazards (PH) regression model will be used. The results will be presented as an adjusted hazard ratio with the corresponding 95% CI.

All regression analyses will be adjusted for the variables being part of the minimisation criteria. If adjustment for all these variables is not possible due to few events (and consequently low power), age (< 70 versus \geq 70) and ICH location will be prioritized.

If the PH assumption is violated, time-dependent covariates will be included.

Since death is a competing risk, we will perform competing risk model as a sensitivity analysis.

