4.3 Withdrawal/loss-to-follow-up

Follow-up will be censored at death (unrelated to an outcome event), last available follow-up (if less than two years), or voluntary withdrawal from the trial.

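### Kaplan-Meier curves and life tables that censor death overstate the absolute risk of recurrent sICH and of the ischaemic and haemorrhagic composites; cumulative incidence should be shown instead

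*SAP*

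**What the plan says.** Section 5.1.1 sets the censoring rule for the primary outcome: "Those not experiencing the event will be censored at last available follow-up, death unrelated to a primary outcome or voluntary withdrawal from the trial". Section 4.3 gives the same rule for follow-up in general. A fatal sICH counts as an event, so the censored deaths are those from other causes.

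Section 5.2.1 describes the group comparison on the primary outcome: "This will be assessed by generating life tables, Kaplan-Meier curves and applying log-rank test". It adds a Cox model for the adjusted hazard ratio with its 95% CI, and then states: "Since death is a competing risk, we will perform competing risk model as a sensitivity analysis". It does not name the type of model and does not mention cumulative incidence.

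For the secondary outcomes, section 5.1.2.1 says that time to event, apart from the modified Rankin Scale, "will be defined in the same way as for primary outcome". Section 5.2.2 analyses the composites "using the same statistical approach as primary outcome, i.e. by Kaplan-Meier curves, log-rank test, and Cox PH model". The competing-risk model is not in that list.

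The outcomes that stand outside the composites are "functional outcome at two years (according to modified Rankin Scale) and death of any cause". MACE includes vascular death, and the haemorrhagic composite includes haemorrhage leading to death. All time-to-event outcomes are analysed at two years and again over total follow-up.

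**The concern.** With death censored, one minus Kaplan-Meier (1-KM) estimates the risk in a hypothetical population in which nobody dies of anything else. It is not the probability that a participant has the event, and it exceeds that probability whenever competing deaths occur. The SAP recognises the competing risk, but the only time-to-event displays it names take no account of it.

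The harm and benefit of antithrombotic drugs here are naturally weighed in absolute terms. Section 2.1 describes the question as safety and efficacy, and section 2.4 sets an unacceptable rise in recurrent sICH against plausible benefit on ischaemic events. A reader who takes two-year risks from the planned curves would find both sides too large. The ischaemic side rests on secondary composites, for which no competing-risk analysis is listed.

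**Working it through.** **Figures in the SAP.** The SAP states no absolute risk from these curves and no mortality after randomisation, so there is no planned figure on this point to reproduce. The usable inputs are the annual sICH rates of 2% and 8% (section 2.4) and the two-year horizon (section 5.2.1).

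**Assumptions.** Hazards are constant. Competing death, meaning death that is not part of the outcome, is taken as 2% to 20% a year, equal in both arms.

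**Formulas.** With annual event rate *r*, annual competing death rate *m* and horizon *T*:
- λ = −ln(1 − r) and μ = −ln(1 − m)
- 1-KM = 1 − exp(−λT)
- Cumulative incidence = λ/(λ + μ) × [1 − exp(−(λ + μ)T)]

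**Kaplan-Meier at two years.** This does not depend on *m*: 1 − 0.98² = 3.96% and 1 − 0.92² = 15.36%, a difference of 11.40 points.

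**Worked case, r = 8%, m = 10%.** λ = 0.0834, μ = 0.1054 and λ + μ = 0.1887. Cumulative incidence = 0.4418 × (1 − exp(−0.3775)) = 0.4418 × 0.3144 = 13.89%. The excess of 1-KM is 15.36 − 13.89 = 1.47 points, and 1.47/13.89 = 10.6% relative.

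**Two-year results.** The excess of 1-KM is in percentage points, with the relative excess in brackets.

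| Competing death per year | Cumulative incidence, 2%/yr sICH | Excess of 1-KM | Cumulative incidence, 8%/yr sICH | Excess of 1-KM | Difference between the two risks (points) |
|---|---|---|---|---|---|
| 2% | 3.88% | 0.08 (2.0%) | 15.06% | 0.30 (2.0%) | 11.18 |
| 5% | 3.76% | 0.20 (5.2%) | 14.62% | 0.74 (5.1%) | 10.86 |
| 10% | 3.57% | 0.39 (10.8%) | 13.89% | 1.47 (10.6%) | 10.32 |
| 15% | 3.38% | 0.58 (17.0%) | 13.17% | 2.19 (16.6%) | 9.79 |
| 20% | 3.20% | 0.76 (23.8%) | 12.47% | 2.89 (23.2%) | 9.27 |

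**Longer follow-up.** The SAP does not state the length of total follow-up, so five years is used as an illustration. At 10% competing death a year, 1-KM is 9.61% against 7.50% (2%/yr sICH) and 34.09% against 26.98% (8%/yr). Over the whole 2% to 20% range, the relative excess runs from about 5% to 64% and from about 5% to 60% respectively.

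**A commoner composite.** For an assumed 10% annual event rate and 10% competing death, 1-KM is 19.0% against 17.2% at two years, and 41.0% against 32.6% at five.

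**Outcome by outcome.** For sICH, deaths from other causes compete. For major ischaemic events, any death not itself due to a listed event competes. For major haemorrhagic events, deaths from haemorrhage are events and the rest compete. For MACE, only non-vascular death competes, so the lower rows of the table are the less relevant ones. For death of any cause nothing competes, and 1-KM is correct.

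**The case against.** The strongest reply is that the planned inference is sound. The log-rank test and the Cox model with death censored address the cause-specific hazard, and the effect estimate that section 5.2.1 names is a hazard ratio. No section says that a two-year risk or risk difference will be read from the curves. The 2% and 8% in section 2.4 are annual rates used to size the trial, not a decision rule. All of this stands. A reader might infer that the primary result is invalid or that the hazard ratio is biased; the documents do not support that.

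A reader might also infer that the SAP ignores competing risk for the primary outcome. It does not: it plans a sensitivity model, and common models of that kind can yield cumulative incidence. The gap is that the type is unnamed and no such display is promised. Nor are all secondary outcomes overstated, since death of any cause is free of the problem and MACE is less affected.

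For the secondary composites, the reference in section 5.2.2 to the same approach as for the primary outcome could be taken to include the sensitivity model. The list that follows spells the approach out without it, so the wording at least needs settling.

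On size, relative comparisons barely move if mortality is equal in the arms: 15.36/3.96 = 3.88 by 1-KM against 13.89/3.57 = 3.89 by cumulative incidence at 10% competing death. Sampling error may also be larger than the bias. If the planned 500 split evenly over the two trials and their arms (125 per arm, an assumption), a simple 95% CI half-width is 1.96 × √(0.04 × 0.96/125) = 3.4 points at 4% risk and 1.96 × √(0.15 × 0.85/125) = 6.3 points at 15%. These arguments limit the size of the point. They do not remove it: absolute differences do shrink, and the error is systematic, in a known direction and avoidable.

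**Conclusion.** The concern holds for absolute risks only. The planned life tables and Kaplan-Meier curves, read as probabilities, overstate recurrent sICH and the ischaemic and haemorrhagic composites, although the SAP itself names death as a competing risk. Over two years the overstatement is about 2% to 24% relative, which is under 1 point at 2% sICH a year and 0.3 to 2.9 points at 8%. The top of that range needs 20% competing death a year. Longer follow-up makes it larger.

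The direction is certain whenever competing deaths occur. The size is not known from the documents, because it rests on assumed mortality and constant hazards. The hazard comparison stands as planned. This is a cheap improvement to the presentation of results and to the specification of the competing-risk analysis, not a flaw in the primary test.

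**What to change.** In sections 5.2.1 and 5.2.2:

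- Present absolute risks by arm as Aalen-Johansen cumulative incidence, for sICH and for each composite, with death that is not part of that outcome as the competing event. State for each composite which deaths count as events and which compete.
- Preferably add the two-year risk difference with its 95% CI. This goes beyond correcting the display, but it gives the harm-benefit comparison directly.
- Keep the log-rank test and cause-specific Cox model for the comparison, and keep Kaplan-Meier for death of any cause.
- Name the competing-risk model (for example, a Fine-Gray subdistribution hazard model), and state that it also applies to the secondary composites.

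The cost is a change of SAP wording, a little more analysis work and slightly lower displayed risks. No new data are needed, and the hazard ratio and its test do not change.

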2.3.1 Minimisation criteria in randomisation algorithm

- Age
 - o < 70 versus \geq 70 years
- Index sICH location
 - o Only supratentorial lobar regions are affected; yes versus no
- Probability of a good outcome at six months (10)
 - o < 0.15 versus \geq 0.15
- Days from index sICH to randomisation
 - o 0 to 6 days versus 7 to 30 days versus > 30 days
- Antiplatelet drug the patient's physician would use if allocated (this criterion only applies to the antiplatelet trial)
 - o Aspirin only; yes versus no

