2.4 Sample size

The sample size estimation was made before the initiation of the study. A fourfold increase in the annual rate of recurrent sICH on antithrombotic drugs (from 2% to 8%) was considered unacceptable and higher than any plausible beneficial effect antithrombotic drugs would have on ischaemic events.

With power of 80% and a 5% significance level to detect an increase of the annual rate of recurrent sICH from 2% to 8% with antithrombotic therapy, the sample size was estimated to 500 participants randomised to intervention versus control. The sample size estimation was made for the trial as a whole, and not as two separate trials investigating the effect and safety of antiplatelets and effect and safety of anticoagulants as two separate trials. No sample size estimation for the two separate trials was performed. Regardless of this, analyses will be made for antiplatelet treatment versus control and anticoagulant treatment versus control separately.

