3.2 Confidence intervals and p-values

The results with p-values below 0.05 will be considered statistically significant, unless otherwise specified. The differences between the groups will be presented with 95% confidence intervals (CIs). All statistical tests will be two-sided.

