5.2.3 Exploratory analyses

If appropriate, primary and secondary outcomes will be compared between subgroups of patients defined by median age, timing of treatment initiation (0 to 6 days, 7 to 30 days and \geq 31 days) and haemorrhage location (lobar versus non-lobar). For participants randomised to anticoagulants versus control, relevant subgroups also include CHA²DS²VASc score (median score as cut-off) and HAS-BLED score (median score as cut-off). The same statistical analyses as described above will be applied.

If low power, we will only present descriptive numbers and not statistical tests.

5.2.4 Hierarchical structure:

Since the study is multicentre, data might exhibit a hierarchical structure with some degree of cluster effect within study centres. The intra-class correlation coefficient (ICC) will be estimated to assess the possible cluster effect in all outcome variables. If ICC will show to be non-negligible suitable adjustment of statistical methods specified above will be applied through inclusion of random effects on study centre into the considered models. In such a

case, frailty models (Cox PH model with fixed and random effects) and generalized linear mixed models will be estimated instead of Cox PH model and ordinal regression model, respectively.

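### Age enters the regression models cut at 70 although it is held in years, and predicted outcome probably enters cut at 0.15; linear terms cost no extra parameter and would give a small gain, mainly for the modified Rankin Scale

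*SAP*

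**What the plan says.** Section 5.2.1 states: "All regression analyses will be adjusted for the variables being part of the minimisation criteria". Section 2.3.1 gives those variables in allocation form only:

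- age, split at 70;
- "Probability of a good outcome at six months (10" (the 10 is a citation number), split at 0.15;
- whether only lobar regions are affected, yes or no;
- days since the index haemorrhage, in three classes;
- in the antiplatelet part only, whether aspirin alone is planned, yes or no.

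Section 5.2.1 states a coding in one place, the fallback for few events, which begins: "If adjustment for all these variables is not possible due to few events (and consequently low power), age (< 70 versus". The second age class is 70 or older, and the other variable kept in that fallback is the location of the haemorrhage. Section 5.2.2 carries the adjustment to the secondary outcomes: "Adjustments for covariates will be performed in the same manner as for primary analysis".

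Section 5.2.3 plans "subgroups of patients defined by median age". A median can be found only if age is recorded more finely than in two classes. Section 4.4.1 lists age among the baseline variables to be reported but does not name the predicted probability. The SAP gives no reason for cutting either variable in a regression and no distribution for either.

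**The concern.** Minimisation needs categories; a regression model does not. With age cut at 70, a participant of 71 is treated as having the same prognosis as one of 90, and a different prognosis from one of 69. Whatever age predicts within each class is left in the unexplained variation.

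For outcomes that age and predicted recovery are likely to predict well (the modified Rankin Scale, death from any cause, MACE), that gives up some precision. In non-linear models it also pulls the treatment estimate slightly towards no effect. The SAP's worry about few events does not justify the cut, because a straight-line term uses one parameter, as a two-class term does. When only two covariates can be kept, each should carry as much information as it can. The trial is analysed as two separate parts, and section 2.4 says that neither was sized, so even a modest gain is worth having.

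**Working it through.** **1. The plan's own figure.** The only computed figure is the 500 in section 2.4 (2% v 8%, power 80%, 5% level; section 3.2 makes tests two-sided). Per arm, n = [1.960·√(2·0.05·0.95) + 0.842·√(0.02·0.98 + 0.08·0.92)]² / 0.06² = 206, or 412 in total. With continuity correction it is 239 per arm, or 478. The gap to 500 may be an unstated allowance or rounding. Covariate coding does not enter this calculation, so it has no bearing here.

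**2. Parameters.** Counting treatment, the antiplatelet model has 1 (treatment) + 1 (age) + 1 (location) + 1 (predicted outcome) + 2 (days) + 1 (aspirin) = 7. The anticoagulant model has 6 and the reduced model 3. Replacing the two-class terms for age and predicted outcome by linear terms leaves all three counts unchanged. Splines would add parameters.

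**3. Information kept by a cut.** For a normal covariate with a linear effect and a share p below the cut, the share of its linear information kept is φ(z)² / [p(1−p)], where z is the normal quantile of p. The SAP gives no distributions, so all values of p are assumptions.

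| Covariate and assumption | p below cut | Kept | Lost |
|---|---|---|---|
| Age, mean 72, SD 10 | 0.42 | 63% | 37% |
| Age, mean 74, SD 10 | 0.34 | 60% | 40% |
| Age, mean 76, SD 9 | 0.25 | 54% | 46% |
| Predicted logit | 0.22 | 51% | 49% |
| Predicted logit | 0.12 | 38% | 62% |

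Worked example for age, mean 76, SD 9: z = (70 − 76)/9 = −0.667, p = 0.252, φ(z) = 0.3194, so 0.3194² / (0.252 × 0.748) = 0.54. Over all splits from 50/50 to 10/90 the loss runs from 36% to 66%.

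**4. Effect on treatment, modified Rankin Scale.** This was simulated with a 7-level proportional-odds outcome, 250 participants (assumed; the SAP gives no size for either part) and a treatment log odds ratio of 0.5. The ratio of squared mean z, linear over cut, is the relative effective sample size.

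- 500 samples: 1.11 with covariate effects of 0.5 and 0.6 per SD, and 1.04 with 0.35 and 0.45. Power rose by 2 to 4 points (55% to 57% in one setting, 58% to 62% in the other).
- A separate run of 300 samples, with 34% and 17% below the cuts: 1.10 with stronger effects (power 58% to 62%) and 1.03 with weaker ones (60% to 61%).

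With 500 samples the standard error of one power estimate is about √(0.25/500) = 2.2 points. The power differences are therefore rough; the error of the differences was not computed.

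**5. Effect on treatment, recurrent haemorrhage.** This was a Cox simulation with 500 participants, two years, a control rate of 2% per year, 400 runs per setting, and two covariates entered either linearly or cut at their 30th and 20th percentiles.

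| Covariate log HR per SD | Power at HR 2, linear v cut | Power at HR 3, linear v cut |
|---|---|---|
| 0.2 | 45% v 44% | 90% v 91% |
| 0.4 | 46% v 46% | 88% v 86% |
| 0.7 | 42% v 40% | 87% v 82% |

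The standard error of the treatment log hazard ratio differed by under 1%. In the last row at HR 3 the difference comes from the estimate (1.07 linear v 1.04 cut; the true value is ln 3 = 1.10). Simulation error is up to about 2.5 points per power estimate.

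**6. Log-rank test.** It uses no covariates, so coding cannot affect it.

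**The case against.** The strongest reply is that nothing here is wrong. Adjusting for the minimisation factors in the form used to allocate is valid, and imbalance within a category is chance imbalance that the confidence interval already covers. This stands: the point concerns efficiency, not bias or error control.

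The prognosis half is weaker than the age half, and this also stands. No sentence says that predicted outcome enters the models cut at 0.15; the cut appears only as an allocation rule. The SAP does not say that the underlying probability was stored, and the variable is not among those prioritised when events are few.

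A reader might infer that about half the information is lost. That does not fit age, where the loss is 37-46% under the assumptions used. More importantly, the loss is in what the covariate says about prognosis, not in what the trial says about treatment. A reader might also infer that the primary result suffers. The log-rank test is untouched, and the Cox results show 0-2 points of power for weak to moderate covariates. A difference of about 5 points needs two strong ones.

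Finally, days to randomisation is also continuous, and its three classes cost two parameters, so leaving it cut may look inconsistent. But eligibility starts at 24 hours and the last class has no upper limit, so a straight line is harder to defend there than for age.

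**Conclusion.** The point holds for age and, conditionally, for predicted outcome, as a cheap improvement. Age is explicitly dichotomised in the reduced model and by natural reading in the full one, it is available in years, and a linear term costs the same single parameter. For predicted outcome the coding is inferred, and the gain depends on the value having been stored.

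The likely benefit is about 3-11% in effective sample size for the modified Rankin Scale. It rests on 250 participants per part, the stated covariate effects, roughly normal covariates and linear effects, none of which comes from the SAP. Death and MACE may gain something, but neither was simulated. Little change is expected in the hazard ratio for recurrent haemorrhage. The documents do not support any claim that the planned adjustment is invalid or that it materially weakens the primary comparison.

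**What to change.** Add to section 5.2.1:

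> Age enters all regression models, including the reduced model, as a continuous covariate in years. The predicted probability of a good outcome enters on the logit scale if its continuous value is stored, and otherwise as the allocation category. The other minimisation variables enter as categories. A sensitivity analysis uses the allocation categories for all variables.

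Section 5.2.2 then needs no change, since it refers back to 5.2.1. Before the wording is fixed, the sponsor should confirm that the predicted probability itself, and not only its class, is in the database.

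The cost is a few lines of SAP text and one extra model run per outcome; no new data are needed for age. The downside is that a linear effect is assumed for age and for the logit. If the true relation is closer to a step, the continuous term could do worse than the category, and the sensitivity analysis would show it.
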